3.1. Primary Objectives

To determine the safety of multiple doses of LT3001 drug product in subjects with AIS.

3.2. Secondary Objectives

To determine the efficacy of multiple doses of LT3001 drug product in subjects with AIS.

This document is confidential.

SAP text Version: Final v1.0 (30-Jun-2025)

Filing requirements: TMF

Page 10 of 55

4. Study Design

4.1. Brief Description

This is a multicenter, double-blind, randomized, and placebo-controlled prospective Phase II clinical study, designed to evaluate LT3001 drug product versus placebo in subjects with AIS. The study is planned to take place in multiple countries. Subjects who participate in this trial should be treated with standard of care of AIS therapies when appropriate.

Approximately 200 eligible subjects will be randomized centrally 1:1 to LT3001 drug product or placebo with the stratification factors. Randomization will be stratified according to age [REDACTED], baseline NIHSS [REDACTED], and time of AIS symptoms onset to the 1st IP [REDACTED]

[REDACTED]

[REDACTED]

Each eligible subject will [REDACTED] The first dose of LT3001 drug product or placebo (1st IP) will be administered within 24 hours after stroke symptoms onset. [REDACTED]

[REDACTED]

LT3001 drug product or placebo will be administered [REDACTED].

A Data Safety Monitoring Board (DSMB) will be formed to assess all data (including imaging data) of LT3001 drug product or placebo treatment. [REDACTED] The DSMB will review safety and efficacy data when the thirtieth treated subject has completed study procedures on Day 7 or terminated the study before Day 7. The DSMB will meet after the data presentation and will issue recommendations relating to safety and study conduct. Unscheduled meetings will be recommended and initiated by the Sponsor or the Principal Investigators. [REDACTED]

[REDACTED]

[figure not shown]
[REDACTED]

[REDACTED]

The participation for each subject is approximately 92 days from the Screening (Visit 1) to the last visit.

This document is confidential.

Study Design

4.2. Subject Selection

4.2.1. Inclusion Criteria

Individuals must meet all of the following criteria to be included in the study:

1. Subject has been diagnosed with AIS
2. Subject or if applicable subject's legally acceptable representative/ legally designated representative consents to participation by signing the informed consent form after receiving full information about the study.
3. Subject [REDACTED] is aged 18 to 90 years (inclusive) [REDACTED]
[REDACTED] is aged 18 to 80 years (inclusive) at the time of Screening (Visit 1).
4. Subject has an NIHSS of 4 to 25.
5. Subject [REDACTED] is able to receive
the 1st IP within 24 hours after stroke symptoms onset
[REDACTED]
[REDACTED]
6. Subjects who are women of childbearing potential, or men whose sexual partners are women of childbearing potential, are able and willing to use at least 1 highly effective method of contraception during the study until 3 months after the last dosing of IP administration.

Neuroimaging Inclusion Criteria:

1. Subject has adequate renal function, has no history of severe allergic reactions to contrast agents, and is able to undergo a contrast brain perfusion with either MRI or computed tomography (CT).
2. [REDACTED]
[REDACTED] the subsequent subjects must adhere to the following
Mismatch Profile on MRI (perfusion is included) or CTP [REDACTED]
[REDACTED] **

** The mismatch ratio is determined in real time by site routine practice (e.g., RAPID or similar software, or other similar analyses) based on the difference between the ischemic core lesion volume and the Tmax >6s lesion volume. If both a multimodal MRI and CTP are performed before enrollment, the later of the 2 scans is assessed to determine eligibility.

4.2.2. Exclusion Criteria

[figure not shown]
[figure not shown]
Individuals meeting any of the following criteria at Screening (Visit 1) or Baseline are ineligible to participate in this study:

This document is confidential.

1. During the current AIS episode, the subject has received or is scheduled to receive EVT and/or intravenous thrombolytic (e.g., recombinant tissue-type plasminogen activator) treatment based on the investigator's assessment of its potential benefit.
2. Subject has a pre-stroke disability (mRS >2).
3. Subject has Alberta Stroke Program Early CT Score of ≤5.
4. Subject has symptoms of suspected subarachnoid hemorrhage, even if CT is normal.
5. Subject has imaging evidence of acute intracranial hemorrhage, intracranial tumor (except meningioma without parenchymal mass effect), arteriovenous malformations, other central nervous system lesions that could increase the risk of bleeding, or aneurysm requiring treatment.
6. Subject has significant mass effect with midline shift.
7. Subject has pre-existing medical, neurological, or psychiatric disease that would confound the neurological or functional evaluations, e.g., seizures at onset of the current AIS, dementia.
8. Subject has current uncontrolled hypertension despite treatment: systolic blood pressure >185 mmHg or diastolic blood pressure >110 mmHg before dosing at Screening (Visit 1).
9. Subject has hemorrhagic diathesis, coagulation factor deficiency or recent oral anticoagulant therapy with International Normalized Ratio >1.7 or activated partial thromboplastin time >1.5 times of upper limit of normal range at Screening (Visit 1).
10. Subject has received conventional heparin within 48 hours before the 1st IP administration, except for low dose subcutaneous conventional heparin or low molecular weight heparin at a preventive dose.
11. Subject has received one of the new oral anticoagulants within 48 hours before the 1st IP administration, e.g., dabigatran, apixaban, rivaroxaban, and edoxaban, except for dabigatran-treated subject who has been given a reversal agent, idarucizumab, before the 1st IP administration.
12. Subject has platelet count <100,000/mm³ at Screening (Visit 1).
13. Subject has blood glucose concentration <50 mg/dL or >400 mg/dL at Screening (Visit 1).
14. Subject has moderate or severe hepatic, renal, and/or active infectious disease at Screening (Visit 1) as judged by the investigator. Subject with confirmed COVID-19 or influenza infection can be enrolled at the investigator's discretion.
15. Subject is lactating, pregnant (pregnancy test required for all female subjects of childbearing potential), or planning to become pregnant during the study.
16. Subject has had history of sICH, prior AIS, myocardial infarction, or serious head trauma within 90 days before Screening (Visit 1).
17. Subject has had any major surgery within 90 days before Screening (Visit 1), e.g., intracranial or intraspinal surgery, coronary artery bypass graft, obstetrical delivery, organ biopsy.
18. Subject has had a bleeding event within 21 days before Screening (Visit 1), e.g., gastrointestinal hemorrhage.
19. Subject has puncture of noncompressible vessels within 7 days before Screening (Visit 1).
20. Subject has a history of severe allergic reactions to LT3001 or excipients.
21. Subject has participated in another investigational study and received IP within 30 days before Screening (Visit 1) or 5 half-lives (whichever is longer).
22. In the opinion of the Investigator, the subject has serious, advanced, or terminal illness that will prevent improvement or follow-up visits.
23. In the opinion of the Investigator, the subject is not appropriate for the study for any other reason.

This document is confidential.

4.3. Determination of Sample Size

4.4. Treatment Assignment and Blinding

The study is placebo-controlled to lessen the risk that events due to chance are falsely attributed to LT3001 drug product.

The study is randomized to control for factors known and unknown between the treatment groups.

The study is blinded so that the subjects, site staff administering the investigational product, and site staff conducting study assessments will not know which treatment a subject receives to allow assessment of the study objectives without bias.

Subjects will be randomly assigned to receive LT3001 drug product or placebo in a ratio of 1:1. The randomization will be stratified according to age [REDACTED], baseline NIHSS [REDACTED], and the time of AIS symptoms onset to the 1st IP [REDACTED]. The stratified randomization is to ensure similar risk distributions [REDACTED].

4.5. Administration of Study Medication

All subjects will receive the first dose of IP within 24 hours after stroke symptoms onset on Day 0 and will

This document is confidential.

be hospitalized for the care of AIS according to each study site's current standard of care. [REDACTED]

[REDACTED]

This document is confidential.

SAP text Version: Final v1.0 (30-Jun-2025)

[REDACTED]

[figure not shown]
Filing requirements: TMF

Page 15 of 55

[figure not shown]
4.6. Study Procedures and Flowchart

Table 1 outlines the timing of procedures and assessments to be performed throughout the study.

Table 1 Schedule of Assessments

This document is confidential.

This document is confidential.

5. Endpoints

5.1. Primary Endpoint

The proportion of subjects with AEs, judged to be probably or definitely related to the IP within 90 days after the 1st IP administration.

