Reference Therapy:	Placebo [REDACTED]
Treatment Duration:	All subjects will receive the first dose of IP within 24 hours after stroke symptoms on Day 0 and will be hospitalized for the care of AIS according to each study site's current standard of care. Each subject will receive [REDACTED] LT3001 drug product or placebo via a 30-minutute intravenous infusion twice within every approximately 24 hours, total 6 doses of IP within approximately 72 hours.  The participation for each subject is approximately 92 days from the Screening (Visit 1) to the last visit.

Efficacy:	Efficacy will be evaluated by assessing the functional outcomes measured by mRS, neurological outcome assessed by NIHSS, the occurrence of recurrent stroke, and cognition assessed by the MoCA; and imaging outcomes measured by change in infarct volume and hypoperfusion lesion.
Safety:	Safety assessments include the occurrence of sICH, aICH, mortality, and AEs.

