In the Phase IIa LT3001-201 study in subjects with AIS, a single dose of LT3001 drug product was generally safe and well tolerated. No subject was reported with symptomatic intracranial hemorrhage (sICH) during the study or within 7 days of receiving IP. Asymptomatic ICH (aICH) was reported in 2 subjects, 1 subject in each treatment arm within 24 hours of receiving IP. Within 7 days of receiving IP, there was a higher proportion of subjects with aICH in the LT3001 drug product group (3 subjects, 18.8%) compared with the placebo group (1 subject, 12.5%), with relative risk (95% confidence interval [CI]) of 1.5 (0.2 to 12.2). No subject died because of intracerebral or other major bleeding complications within 90 days. Eleven SAEs were reported in 6 subjects: 4 subjects (25.0%) in the LT3001 drug product group and 2 subjects (25.0%) in the placebo group, all of which were considered as unrelated or unlikely related to IP. Among these 6 subjects, 2 subjects died because of SAEs. One subject died because of an SAE of pneumonia of severe intensity in the LT3001 drug product group (6.3%) and the other subject died because of an SAE of respiratory arrest of severe intensity in placebo group (12.5%). Among the 11 SAEs, 7 SAEs of severe intensity were reported for 3 subjects (18.8%) in the LT3001 drug product group (pneumonia aspiration for 1 subject, cerebral infarction in a second subject, and pneumonia and bronchial neoplasm in the third subject) and for 1 subject (12.5%) in the placebo group (pneumonia, COVID 19, and respiratory arrest). No subject discontinued the IP because of treatment-emergent AEs. No clinically significant trend was observed for laboratory parameters, vital signs, ECGs, or neurological examinations.

Regarding the efficacy data, the decrease in National Institute of Health Stroke Scale (NIHSS) of  $\geq 4$  points at Visit 5 (Day 30) showed promise: a higher proportion of subjects in the LT3001 drug product group (46.67%) showed decrease in NIHSS of  $\geq 4$  compared with the placebo group (14.29%).

Based on the outcomes of the clinical and nonclinical studies, the safety monitoring plan for this study and future LT3001 clinical studies will include the following:

1. Physical examination.
2. Assessment of vital signs.

3. Clinical laboratory tests including hematology and clinical biochemistry.
4. Coagulation/clotting parameters, including PT, and aPTT.
5. Monitoring of AEs.

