SEVERE: An event that prevents normal everyday activities.

Table 4. Classification of Adverse Events by Relationship to Investigational Product

UNRELATED: This category applies to those AEs that are clearly and incontrovertibly due to extraneous causes (disease, environment, etc).
UNLIKELY: This category applies to those AEs that are judged to be unrelated to the IP but for which no extraneous cause may be found. An AE may be considered unlikely to be related to IP if or when it meets 2 of the following criteria: (1) it does not follow a reasonable temporal sequence from administration of the IP ; (2) it could readily have been produced by the subject's clinical state, environmental or toxic factors, or other modes of therapy administered to the subject; (3) it does not follow a known pattern of response to the IP; or (4) it does not reappear or worsen when the IP is readministered.
POSSIBLY: This category applies to those AEs for which a connection with the IP administration appears unlikely but cannot be ruled out with certainty. An AE may be considered possibly related if or when it meets 2 of the following criteria: (1) it follows a reasonable temporal sequence from administration of the IP; (2) it could not readily have been produced by the subject's clinical state, environmental or toxic factors, or other modes of therapy administered to the subject; or (3) it follows a known pattern of response to the IP.
PROBABLY: This category applies to those AEs that the investigator feels with a high degree of certainty are related to the IP. An AE may be considered probably related if or when it meets 3 of the following criteria: (1) it follows a reasonable temporal sequence from administration of the IP; (2) it could not be reasonably explained by the known characteristics of the subject's clinical state, environmental or toxic factors, or other modes of therapy administered to the subject; (3) it disappears or decreases on cessation or reduction in dose (note that there are exceptions when an AE does not disappear upon discontinuation of the IP, yet drug-relatedness clearly exists; for example, as in bone marrow depression, fixed drug eruptions, or tardive dyskinesia); or (4) it follows a known pattern of response to the IP.

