11.2.4. Adverse Events

An AE is any symptom, physical sign, syndrome, or disease that either emerges during the study or, if present on or after the 1st IP administration [REDACTED], worsens during the study, regardless of the suspected cause of the event. AEs are defined as Treatment-emergent adverse events (TEAEs) in the SAP and TLFs.

An SAE is any untoward medical occurrence, in the view of either the Investigator or Sponsor, that:

- results in death,
- is life-threatening,
- results in inpatient hospitalization or prolongation of existing hospitalization,
- results in persistent or significant disability/incapacity, and/or
- is a congenital anomaly/birth defect

Other important medical events that may not be immediately life-threatening or result in death or hospitalization, based upon appropriate medical judgment, are considered SAEs if they are thought to jeopardize the subject and/or require medical or surgical intervention to prevent one of the outcomes defining an SAE.

This document is confidential.

Also, Related TEAE is an any event deemed possibly, probably or definitely related to treatment.

All AEs will be coded using the actual version of MedDRA dictionary to provide the system organ class (SOC) and preferred term (PT). Duration of the adverse event (AE) will be calculated and presented in days. Duration of the AE is defined as (AE end date – AE start date) + 1.

The number and percentage of subjects as well as number of events will be presented for TEAE summaries. An overall summary of TEAEs including the following categories will be presented:

- at least one TEAE
- at least one serious TEAE
- at least one related TEAE
- at least one TEAE leading to study drug withdrawal
- at least one TEAE with fatal outcome

A summary table of TEAEs by SOC and PT will be presented. Multiple instances of the TEAE in each SOC and multiple occurrences of the same PT are counted only once per subject. The denominator used for calculating the percentages will be the total number of subjects included in the safety population.

In addition, for each of the following, a summary of TEAEs will be produced at the subject level:

- Serious TEAEs by SOC and PT
- TEAEs by worst intensity by SOC, PT
- TEAEs by maximum relationship by SOC, PT
- TEAEs leading to study drug withdrawal

All AEs for each subject, including multiple occurrences of the same event, will be presented in full in a comprehensive listing sorted by subject number.

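### The primary safety endpoint counts only 'probably' or 'definitely' related AEs, so it is insensitive to bleeding, neurological worsening and death; attribution-free between-arm comparisons should stand beside it

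*SAP*

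**What the plan says.** SAP 5.1 defines the primary endpoint as "The proportion of subjects with AEs, judged to be probably or definitely related to the IP within 90 days after the 1st IP administration". Protocol 6.2.1 agrees. SAP 11.1 presents it by arm in the Safety population, with a difference in proportions and a 95% CI described as exact Clopper-Pearson.

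The grades come from Table 4 in protocol 12.7.1. For the second-highest grade, "An AE may be considered probably related if or when it meets 3 of the following criteria". In short, its four criteria are:

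1. plausible timing;
2. "it could not be reasonably explained by the known characteristics of the subject's clinical state" (or by environment or other therapy);
3. "it disappears or decreases on cessation or reduction in dose";
4. a known pattern of response to the product.

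Criterion 3 carries a caveat: "note that there are exceptions when an AE does not disappear upon discontinuation of the IP, yet drug-relatedness clearly exists". 'Definitely' requires all four criteria, with recurrence on re-exposure added to the third if rechallenge occurs.

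Elsewhere the SAP uses a wider definition. Under 11.2.4, "Related TEAE is an any event deemed possibly, probably or definitely related to treatment". That section tabulates related, serious and any TEAEs as counts and percentages.

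SAP 5.2 lists sICH, aICH, all-cause mortality, the number and severity of AEs, and the number of subjects with AEs as secondary safety outcomes. None of these is filtered by attribution.

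**The concern.** The primary objective is the safety of the multiple-dose regimen in acute stroke. The natural course of stroke produces some of the same events a drug with thrombolytic activity might cause: haemorrhagic change, neurological decline and death. A blinded investigator judging one patient can seldom tell the two sources apart. Comparing randomized arms can. Protocol 9.3 gives a related reason for the placebo arm: to guard against chance events being wrongly blamed on the drug.

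The primary endpoint applies case-by-case judgement before the arms are compared, and Table 4 pushes stroke-explainable events below the counting threshold. The two arms could look alike on the primary result while differing on bleeding or death. The visible text does not say how the primary proportion is to be read alongside the unfiltered outcomes. For related, any and serious TEAEs it shows no between-arm difference or interval.

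**Working it through.** **Inputs.** About 200 subjects randomized 1:1, so about 100 per arm (SAP 4.1). Table 4 thresholds (protocol 12.7.1). Dosing: "total 6 doses of IP within approximately 72 hours" (protocol synopsis, Treatment Duration). Earlier attribution data (protocol 5.3 and 7.2). No expected rate for the primary endpoint is visible, and the sample-size text in protocol 13.1 and SAP 4.3 is not shown, so the choice of 200 cannot be reproduced.

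**A documented figure that can be reproduced.** Protocol 5.3 reports aICH within 7 days in the earlier stroke study as 3 (18.8%) v 1 (12.5%), that is 3/16 v 1/8. RR = (3/16)/(1/8) = 1.5. SE(log RR) = √(1/3 − 1/16 + 1/1 − 1/8) = 1.070. 95% CI = exp(0.405 ± 1.96 × 1.070) = 0.18 to 12.2. This matches the stated 1.5 (0.2 to 12.2).

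**Table 4, all 16 patterns of four yes/no criteria.**

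- Three or more met: 5 patterns qualify as at least 'probably'.
- Criterion 2 fails because the stroke explains the event: 1 of the remaining 8 qualifies (1+3+4), and 'definitely' is impossible.
- Criterion 2 fails together with 3 or with 4: none qualifies.

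**Applied to an early intracranial bleed.** Timing is met. Criterion 2 fails, since acute stroke is a reasonable explanation. If the bleed does not recede on stopping, criterion 3 fails unless the caveat is used. Criterion 4 is hard to claim, because protocol 5.4 presents LT3001 as leaving bleeding time unchanged and showing no sign of more intracranial bleeding.

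- With 4 granted and 3 not: 2 of 4. Timing plus pattern gives 'possibly', which is not counted.
- With 4 not granted: at most 2 of 4, even if the caveat is used for 3. The bleed also meets two 'unlikely' criteria (clinical state could have produced it; no known pattern).

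Stroke-explained neurological worsening follows the same path. A death can show no improvement on stopping, so if the stroke explains it, only the caveat is left.

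**Late events.** Dosing ends at about Day 3, leaving about 90 − 3 = 87 days in which a new-onset AE offers no dose to stop. Without the caveat it needs 1+2+4, which a stroke-explainable event cannot meet.

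**Programme record.** Of the 11 SAEs in the earlier stroke study, "all of which were considered as unrelated or unlikely related to IP". Protocol 7.2 says the same of all AEs in the multiple-dose Phase I studies. The first-in-human headache was 'possibly'. This points to a low rate but does not prove one. LT3001-103 had 3/0.30 = 10 and 6/0.545 = 11 treated subjects, and 0/21 has an exact 95% upper limit of 16%.

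**Precision at 100 per arm.** Exact upper limit for 0/100 = 1 − 0.025^(1/100) = 3.6%. For 1/100 the interval is 0.03% to 5.4%; for 2/100 it is 0.2% to 7.0%. Against zero placebo events, two-sided Fisher p is 0.059 for 5 active events and 0.029 for 6. (The 0.05 level is an assumption; the plan is descriptive.)

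**How attribution dilutes a difference.** Assume sICH of 2% v 8%, and let f be the share graded 'probably' or higher, equal in both arms because of blinding. The excess reaching the primary endpoint per 100 is 6 × f:

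| f | excess per 100 |
|---|---|
| 1 | 6 |
| 0.5 | 3 |
| 0.25 | 1.5 |
| 0.1 | 0.6 |
| 0 | 0 |

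At f = 0.25 the rates become 0.5% v 2%. Exact Fisher power falls from 37% for the unfiltered comparison to 1% (normal approximation: 50% to 16%).

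**What an unfiltered comparison gives.** With 12.5% v 18.75% and 100 per arm, about 31 subjects have an event. SE = √(0.125 × 0.875/100 + 0.1875 × 0.8125/100) = 0.0512, so the difference is 6.25 points, 95% CI about −3.8 to +16.3. Power is 18% (Fisher) to 23% (z). That is informative as description, not as a test.

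**The case against.** A reader might infer that the endpoint is near zero by construction, or that it would read 0 v 0 whatever the drug did. The documents do not support that. Any AE can count. Hypersensitivity or infusion-site reactions can qualify through 1+2+4. The transient blood-pressure falls seen in animals (protocol 5.2.1), if they occurred in patients, could qualify through 1+3+4 even with stroke as an alternative cause. Table 4 is permissively worded, criterion 3 has its written caveat, and no expected rate is visible. The stroke-study record reported covers SAEs only, after a single dose. SAP 8.3 also sets a missing relationship to 'related' without naming a grade, which could add events; SAP 11 says missing safety data are not imputed, so the two need reconciling.

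A second tempting inference is that harm would go unseen. It would not. sICH, aICH and mortality are tabulated by arm regardless of cause, and the DSMB reviews safety and imaging data. The analysis text for these outcomes is partly redacted (SAP 11.2.1 to 11.2.3), so between-arm differences may already be planned there.

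It is also fair that the trial is exploratory, that no pass/fail rule is visible, and that nothing says a low proportion will be called safe. SAP 11.2.4 already tabulates at-least-possibly-related TEAEs and TEAEs by maximum relationship.

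These objections limit the point but do not remove it. The Table 4 logic for stroke-explainable events stands, the primary threshold is narrower than the SAP's own definition of related, and the visible plan gives no difference or interval for related, any or serious TEAEs.

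**Conclusion.** The point holds as a limitation of what is made primary and compared. The primary proportion should be expected to be low, and it responds poorly to intracranial bleeding, neurological worsening and death, because a stroke-explainable event has one route to 'probably' and none to 'definitely'. At about 100 per arm, even zero events leaves up to 3.6% compatible with the data, and a real excess of bleeding reaches the endpoint only in proportion to the share graded up.

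This assumes that investigators follow Table 4 as written and regard the stroke as a reasonable explanation. The 2% v 8% and the values of f are illustrative. The conclusion does not extend to AEs unrelated to the stroke, and it does not imply that safety data go uncollected. It is an inexpensive improvement to make before database lock, not a reason to replace the endpoint.

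**What to change.** Keep the primary endpoint. In SAP 11.1 and 11.2.4, before database lock:

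- Add the LT3001-minus-placebo difference with a named two-sample 95% CI (for example Miettinen-Nurminen; Clopper-Pearson is a single-proportion interval) for (a) subjects with at least one at-least-possibly-related TEAE and (b) subjects with any TEAE and with any serious TEAE, regardless of causality.
- Show these beside sICH, aICH and all-cause mortality, giving the same difference and CI there if the redacted text does not already provide it.
- State that the primary proportion will be interpreted together with these attribution-free comparisons, and that a low primary proportion alone will not be taken as evidence of safety.

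The sponsor should not rest the primary conclusion wholly on the secondary comparisons: they are unranked and not powered.

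Cost: SAP wording and a few table columns, with no new data. Displayed rates will be higher in both arms because background stroke events are included, and at about 100 per arm the intervals will be wide and descriptive only.
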